#### **10.3 Visit 3- 2 weeks post-procedure**

1. Record any Adverse Experiences and Review subject diary for adverse experiences and dosing compliance.
2. Record changes to concomitant medications.
3. Perform abbreviated physical examination.
4. Perform and record vital signs.
5. Perform and record oximetry.
6. Perform post-op survey (see separate document for study tool).
7. Review pill bottles for medication usage.

#### **10.4 Visit 4 – 1 month post-procedure**

1. Record any Adverse Experiences and Review subject diary for adverse experiences and dosing compliance.
2. Record changes to concomitant medications.
3. Perform abbreviated physical examination.
4. Perform and record vital signs.
5. Perform and record oximetry.
6. Perform post-op survey (see separate document for study tool).
7. Review pill bottles for medication usage.

#### **10.5 Visit 5- 3 months post-procedure**

1. Record any Adverse Experiences and Review subject diary for adverse experiences and dosing compliance.
2. Record changes to concomitant medications.
3. Perform abbreviated physical examination.
4. Perform and record vital signs.
5. Perform and record oximetry.
6. Perform post-op survey (see separate document for study tool).
7. Review pill bottles for medication usage.

#### **10.6 Visit 6- 1 year post-procedure**

1. Record any Adverse Experiences and Review subject diary for adverse experiences and dosing compliance.
2. Record changes to concomitant medications.
3. Perform abbreviated physical examination.
4. Perform and record vital signs.
5. Perform and record oximetry.
6. Perform post-op survey (see separate document for study tool).

7. Review pill bottles for medication usage.

### **10.7 Early Withdrawal Visit**

1. Record any Adverse Experiences and Review subject diary for adverse experiences and dosing compliance.
2. Record changes to concomitant medications.
3. Perform abbreviated physical examination.
4. Perform and record vital signs.
5. Perform and record oximetry.
6. Perform post-op survey (see separate document for study tool).
7. Review pill bottles for medication usage.

## **11 ADVERSE EXPERIENCE REPORTING AND DOCUMENTATION**

### **11.1 Adverse Events**

An adverse event (AE) is any untoward medical occurrence in a clinical investigation of a patient administered a pharmaceutical product and that does not necessarily have a causal relationship with the treatment. An AE is therefore any unfavorable and unintended sign (including an abnormal laboratory finding), symptom or disease temporally associated with the administration of an investigational product, whether or not related to that investigational product. An unexpected AE is one of a type not identified in nature, severity, or frequency in the current Investigator's Brochure or of greater severity or frequency than expected based on the information in the Investigator's Brochure.

The Investigator will probe, via discussion with the subject, for the occurrence of AEs during each subject visit and record the information in the site's source documents. Adverse events will be recorded in the patient CRF. Adverse events will be described by duration (start and stop dates and times), severity, outcome, treatment and relation to study drug, or if unrelated, the cause.

#### **AE Severity**

The guidelines shown in Table 1 below should be used to grade severity. It should be pointed out that the term "severe" is a measure of intensity and that a severe AE is not necessarily serious.

**Table 1. AE Severity Grading**

Severity (Toxicity Grade)	Description
Mild (1)	Transient or mild discomfort; no limitation in activity; no medical intervention or therapy required. The subject may be aware of the sign or symptom but tolerates it reasonably well.
Moderate (2)	Mild to moderate limitation in activity, no or minimal medical intervention/therapy required.
Severe (3)	Marked limitation in activity, medical intervention/therapy required, hospitalizations possible.
Life-threatening (4)	The subject is at risk of death due to the adverse experience as it occurred. This does not refer to an experience that hypothetically might have caused death if it were more severe.

### AE Relationship to Study Drug

The relationship of an AE to the study drug should be assessed using the following the guidelines in Table 2.

**Table 2. AE Relationship to Study Drug**

Relationship to Drug	Comment
Definitely	Previously known toxicity of agent; or an event that follows a reasonable temporal sequence from administration of the drug; that follows a known or expected response pattern to the suspected drug; that is confirmed by stopping or reducing the dosage of the drug; and that is not explained by any other reasonable hypothesis.
Probably	An event that follows a reasonable temporal sequence from administration of the drug; that follows a known or expected response pattern to the suspected drug; that is confirmed by stopping or reducing the dosage of the drug; and that is unlikely to be explained by the known characteristics of the subject's clinical state or by other interventions.
Possibly	An event that follows a reasonable temporal sequence from administration of the drug; that follows a known or expected response pattern to that suspected drug; but that could readily have been produced by a number of other factors.
Unrelated	An event that can be determined with certainty to have no relationship to the study drug.

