### 8.3 Test and Control Products

#### 8.3.1 Test Product

AtriCure cryosurgical system (AtriCure, Inc., West Chester, Ohio)

The cryoprobe will be applied to the intercostal nerve under thoracoscopic visualization at the level of the incision and 2 interspaces above and below, bilaterally. The temperature and duration of cryoablation therapy is pre-set by the probe and cryosurgical system at 2 minutes to -60°C. Each nerve will receive one cycle of cryoablation.

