#### 8.3.2 Control Product

Thoracic epidural catheter will be placed by the pediatric anesthesia team prior to Nuss procedure. Catheters will be placed using sterile technique at approximately T5-6 or T6-7 interspaces; procedure specifics are dependent on the attending anesthesiologist's patient-dependent preference. Whether the patient will be awake or asleep for epidural placement will be at the discretion of the attending anesthesiologist. After placement, epidural infusion will begin with 0.1% ropivacaine and 2mcg/cc fentanyl. No bolus doses will be used.

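### Table 2's upper relatedness grades need confirmation by stopping or reducing a dosage, which one-time cryoablation cannot supply, and section 5.3's two causality axes are not carried through

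*Combined protocol and SAP*

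**What the plan says.** Section 11.1 gives the instruction: "The relationship of an AE to the study drug should be assessed using the following the guidelines in Table 2". No other relatedness scale appears. Table 2 has four grades.

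- *Definitely* has two routes. It opens with "Previously known toxicity of agent; or an event that follows a reasonable temporal sequence from administration of the drug". The second route goes on to require an expected pattern, no other reasonable explanation, and that the event is one "that is confirmed by stopping or reducing the dosage of the drug".
- *Probably* has one route, with the same stop-or-reduce element joined by *and* to the rest.
- *Possibly* drops that element but covers an event of suitable timing and pattern "but that could readily have been produced by a number of other factors".
- *Unrelated* is "An event that can be determined with certainty to have no relationship to the study drug".

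On the interventions, section 8.3.1 says of the test arm: "Each nerve will receive one cycle of cryoablation". For the control arm, section 8.3.2 describes a one-time act and then a continuing treatment: "Thoracic epidural catheter will be placed by the pediatric anesthesia team prior to Nuss procedure", and "After placement, epidural infusion will begin with 0.1% ropivacaine and 2mcg/cc fentanyl".

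Section 5.3 asks for AEs to be assessed for their relationship to the anesthetic method and, separately, to the procedure. Sections 9.1.6 and 11.1 record the relation to study drug, and 11.1 also asks for a cause when the event is judged unrelated. Section 14.4 tabulates the relationship to study drug by treatment group.

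**The concern.** Table 2 is worded for a drug whose dosage can be lowered or withdrawn. The test treatment is a device applied once during surgery. A scale whose upper grades depend on withdrawal can treat equally well-supported events differently according to which analgesic preceded them, and section 14.4 then sets those grades side by side by arm.

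The object of the assessment is also unsettled. Section 5.3 names two axes, but the recording and tabulation sections name a third object, study drug, which the protocol does not define. Sections 8.5 and 8.6 use the term for medication dispensed to and returned by subjects, and section 8.4 lists study drugs apart from equipment. The AE definition in 11.1 likewise refers to a pharmaceutical product. An assessor could reasonably be unsure whether an effect of cryoablation belongs in that field at all.

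At stake is how the relatedness column can be read in a small trial that compares two analgesic techniques.

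**Working it through.** The plan states no figure on this point, so the check applies Table 2 literally.

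**Assumption.** Table 2 is applied to the assigned analgesic method. If study drug meant only dispensed medication, cryoablation would not be graded at all, and the problem would be the missing axis described in step 4.

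**Step 1: grades by case.** Take an event with reasonable timing and an expected pattern that is not certainly unrelated.

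| Previously known toxicity | Confirmed by stopping or reducing | Other explanation | Grade met |
|---|---|---|---|
| No | No | None reasonable | None of the four |
| No | No | Unlikely | None of the four |
| No | No | Readily available | *Possibly* |
| No | Yes | None reasonable | *Definitely* (also meets *Probably*) |
| No | Yes | Unlikely | *Probably* |
| No | Yes | Readily available | *Possibly* |
| Yes | No | Any | *Definitely*, by the known-toxicity route |

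**Step 2: which rows each treatment can reach.**

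- Cryoablation, event appearing after the cycle: only the rows with *No* in the second column. No dosage remains to be stopped or reduced.
- Act of catheter placement: the same rows, for the same reason.
- Epidural infusion, event while it runs: all rows, provided the infusion is actually reduced or stopped and the event responds.
- Epidural infusion, event first appearing after it has ended: only the *No* rows. The Background section limits epidural use to the first two to three post-operative days, whereas AEs are collected up to the 1-year visit (section 10.6).

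**Step 3: what follows.** *Probably* is out of reach for an event appearing after cryoablation and for one due to placement. *Definitely* is reachable there only as a previously known toxicity. The first two rows are a true gap: too well supported for *Possibly*, not excluded with the certainty that *Unrelated* demands, and barred from the two upper grades by an element that cannot be met.

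**Step 4: the causality object, section by section.**

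| Section | Object of causality |
|---|---|
| 5.3 | Anesthetic method; procedure |
| 9.1.6 | Study drug |
| 11.1, recording | Study drug; a cause if unrelated |
| Table 2 | Study drug, drug or agent |
| 14.4 | Study drug |

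Neither axis of 5.3 has grading criteria in Table 2, and neither is named in the 14.4 tabulation.

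**The case against.** Several points can fairly be made on the other side.

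*Table 2 is guidance.* Section 11.1 says *should* and *guidelines*, so an experienced assessor would choose the nearest grade. That is likely in practice. But the documents give no rule for an event that fits no grade, and section 8.2 says clinicians are not blinded once the group is revealed, so the choice would be improvised with the arm known.

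*The gap is narrow.* The event must follow a known or expected pattern yet not be a previously known toxicity, a distinction the protocol does not draw. It must also lack a ready alternative cause, although every subject has had a Nuss procedure and receives post-operative analgesics. This stands. Many events would go to *Possibly* or to the known-toxicity route; the three epidural risks named in the Background could take the latter. The text gives no such list for cryoanalgesia, but consent pages were removed and may contain one.

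*Study drug may be template wording for the assigned treatment.* Section 15.1 speaks of each subject treated with it, and section 12.1, under a study-drug heading, speaks of study treatment. This is plausible and is the assumption made above. The term remains undefined.

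Three stronger readings are tempting but unsupported. A reader might infer a clean split, with cryoablation events ungradable and epidural events gradable. Placement events and late infusion events share the gap, and an intra-operative event that abated when freezing stopped could in theory meet the element. A reader might infer that section 5.3 has been superseded. Nothing withdraws it; the later sections simply do not repeat its axes, and the 11.1 request for a cause leaves room to note a procedural one, although ungraded and not named in the 14.4 tabulation. A reader might also infer that the safety comparison as a whole is compromised; the verdict explains why it is not.

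**Conclusion.** The point holds as a minor one, wrong as written. Followed literally, Table 2 can leave a well-supported event after cryoablation, or after catheter placement, without any grade, while a comparable event during the epidural infusion can be graded *Definitely* or *Probably*. The by-arm relationship column in 14.4 is therefore not fully like for like. That conclusion rests on applying Table 2 to the assigned analgesic method. The mismatch between 5.3 and the recording and tabulation sections does not depend on that assumption.

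The number of events affected cannot be estimated: the documents give no AE rates, and the synopsis expects little side-effect data from 20 subjects. The effect is confined to one descriptive column. AE incidence is counted irrespective of relatedness. Serious events are documented and reported regardless of causality (sections 11.2.1 and 16.2), individual side effects are listed in a table (synopsis, Statistics), and the length-of-stay analysis does not use relatedness.

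**What to change.** 1. In 9.1.6, 11.1, Table 2 and 14.4, replace *study drug*, *drug* and *agent* as the object of causality with the two axes of section 5.3: the assigned analgesic method (cryoablation, or epidural placement and infusion) and the Nuss procedure.
2. Extend the AE definition in 11.1 from a pharmaceutical product to the study intervention, including the device.
3. In both arms, make response to stopping or reducing treatment supportive evidence where applicable, not a required element of *Definitely* and *Probably*.

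With the third change, the two empty rows in the working become *Definitely* (no other reasonable explanation) and *Probably* (other explanation unlikely). *Possibly* and *Unrelated* keep their meaning, so all four grades are reachable for cryoablation, placement and infusion. One limit remains: an unexpected event that is neither a known toxicity nor certainly unrelated still has no grade, because the expected-pattern element stays.

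The cost is wording, plus a case report form field if it uses the same term (the form is not in the documents). No procedures, visits or patients are added. The downsides are two relatedness entries per AE instead of one, and a slightly less strict standard for the two upper grades. The change belongs in the protocol: section 14 lets a later SAP alter the tabulation, but the criteria by which investigators assign the grades are set in 11.1.

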### 11.2 Serious Adverse Experiences (SAE)

An SAE is defined as any AE occurring at any dose that results in any of the following outcomes:

- death
- a life-threatening adverse experience
- inpatient hospitalization or prolongation of existing hospitalization
- a persistent or significant disability/incapacity
- a congenital anomaly/birth defect

Other important medical events may also be considered an SAE when, based on appropriate medical judgment, they jeopardize the subject or require intervention to prevent one of the outcomes listed.

#### 11.2.1 Serious Adverse Experience Reporting

Study sites will document all SAEs that occur (whether or not related to study drug) per [UCSF CHR Guidelines](#). The collection period for all SAEs will begin after informed consent is obtained and end after procedures for the final study visit have been completed.

In accordance with the standard operating procedures and policies of the local Institutional Review Board (IRB)/Independent Ethics Committee (IEC), the site investigator will report SAEs to the IRB/IEC.

### **11.3 Medical Monitoring**

Contact the Pediatric Surgery team to report medical concerns or questions regarding safety - [contact]. While subjects are inpatient, nursing staff and pediatric surgery service doctors are in-house 24 hours per day, 7 days per week.

## **12 DISCONTINUATION AND REPLACEMENT OF SUBJECTS**

### **12.1 Early Discontinuation of Study Drug**

A subject may be discontinued from study treatment at any time if the subject, the investigator, or the Sponsor feels that it is not in the subject's best interest to continue. The following is a list of possible reasons for study treatment discontinuation:

- Subject withdrawal of consent (or assent)
- Subject is not compliant with study procedures
- Adverse event that in the opinion of the investigator would be in the best interest of the subject to discontinue study treatment
- Protocol violation requiring discontinuation of study treatment
- Lost to follow-up
- Positive pregnancy test (females)

If a subject is withdrawn from treatment due to an adverse event, the subject will be followed and treated by the Investigator until the abnormal parameter or symptom has resolved or stabilized.

All subjects who discontinue study treatment should come in for an early discontinuation visit as soon as possible and then should be encouraged to complete all remaining scheduled visits and procedures.

All subjects are free to withdraw from participation at any time, for any reason, specified or unspecified, and without prejudice.

Reasonable attempts will be made by the investigator to provide a reason for subject withdrawals.

### **12.3 Withdrawal of Subjects from the Study**

A subject may be withdrawn from the study at any time if the subject, the investigator, or the Sponsor feels that it is not in the subject's best interest to continue.

All subjects are free to withdraw from participation at any time, for any reason, specified or unspecified, and without prejudice.

Reasonable attempts will be made by the investigator to provide a reason for subject withdrawals. The reason for the subject's withdrawal from the study will be specified in the subject's source documents. As noted above, subjects who discontinue study treatment early should have an early discontinuation visit.

### **12.4 Replacement of Subjects**

Subjects who withdraw from the study treatment will not be replaced.

Subjects who withdraw from the study will not be replaced.

## 13 PROTOCOL VIOLATIONS

A protocol violation occurs when the subject or investigator fails to adhere to significant protocol requirements affecting the inclusion, exclusion, subject safety and primary endpoint criteria. Protocol violations for this study include, but are not limited to, the following:

- Failure to meet inclusion/exclusion criteria
- Interference with randomization
- Non-compliance with study drug regimen

Failure to comply with Good Clinical Practice (GCP) guidelines will also result in a protocol violation. The investigator will determine if a protocol violation will result in withdrawal of a subject.

When a protocol violation occurs, it will be discussed with the investigator and a Protocol Violation Form detailing the violation will be generated. This form will be signed by a Sponsor representative and the Investigator. A copy of the form will be filed in the site's regulatory binder and in the Sponsor's files.

## 14 STATISTICAL METHODS AND CONSIDERATIONS

Prior to the analysis of the final study data, a detailed Statistical Analysis Plan (SAP) will be written describing all analyses that will be performed. The SAP will contain any modifications to the analysis plan described below.

### 14.1 Data Sets Analyzed

All eligible patients who are randomized into the study and receive at least the initial analgesic application (cryoanalgesia or epidural catheter placement) and undergo Nuss procedure will be included in the analysis.

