## 1 BACKGROUND

Pectus excavatum is the most common congenital chest wall deformity, affecting approximately 1 out of every 1000 live births. It presents as a depression of the anterior chest wall, which can compress the heart and lungs, causing symptoms such as shortness of breath, exercise intolerance, and chest pain. The minimally invasive pectus excavatum repair, known as the Nuss procedure, is a common corrective procedure. It uses an implanted, thoracoscopically-guided convex metal bar to immediately reshape the chest wall. The benefits of this method compared to open repair include smaller incisions, no cartilage resection or osteotomy, and reduced operative times. However, the immediate reshaping of the chest wall results in significant post-operative pain, which can be challenging for patients, families, and clinicians. The ability to adequately control this post-operative pain is the primary determining factor for length of hospitalization following the procedure.

There is no standardized protocol for the management of pain following the Nuss procedure. Epidural analgesia and patient controlled analgesia (PCA) are the two most commonly used techniques, employed either independently or together. Thoracic epidural analgesia has been shown, with limited data, to be more effective than PCA alone for the first few postoperative days, but carries significant risks, including nerve damage, infection, and respiratory depression. Epidural analgesia also reduces post-operative mobility, and often necessitates the use of urinary catheters, which can increase risk of urinary tract infections. The use of epidural analgesia is limited to the first two to three post-operative days, at which time patients must be transitioned to alternate methods. This may increase length of stay, as it introduces an intermediate step prior to home oral regimen.

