### **5 CRITERIA FOR EVALUATION**

#### **5.1 Primary Efficacy Endpoint**

Hospital length of stay, measured from time of surgery to time of discharge

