## 8 STUDY TREATMENTS

### 8.1 Method of Assigning Subjects to Treatment Groups

Prior to enrollment, the patients will be randomly assigned to cryoanalgesia or thoracic epidural groups in a 1:1 ratio using a computerized random sequence generator (<http://www.random.org/>). The values 1-20 are entered in the system, which creates a random sequence of the integers, formatted in 2 columns of 10 integers each. Column 1 is assigned to cryoanalgesia, and column two is assigned to thoracic epidural. The assignments are placed in closed envelopes with the integers on the outside of the envelopes. The study surgeons are blinded to the randomization. As patients are enrolled in the study, they are assigned an integer in order of enrollment (the first patient enrolled is patient 1, the next patient 2, etc.). The envelope associated with each patient number is opened on the morning of surgery, revealing their group assignment.

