### 8.4 Supply of Study Drugs and Equipment at the Site

All study drugs and equipment are regularly stocked in the hospital. Prior to each Nuss procedure, both the AtriCure Cryosurgical system and supplies for thoracic epidural will be made available in the operating room.

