### **10.2 Visit 2- Surgery and Post-operative hospitalization**

Time of Surgery

1. Urine pregnancy test (females)
2. Open randomization allocation envelope
3. Initial analgesic application (cryoanalgesia or epidural) and Nuss procedure

According to inpatient unit protocol

1. Perform and record vital signs.
2. Perform and record oximetry.

Once per day while inpatient

1. Concomitant medications review.
2. Perform abbreviated physical examination.

Twice-per-day study visits while inpatient

1. Record any Adverse Experiences
2. Administer inpatient survey (see separate document)

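### Section 14.1 leaves out a randomised epidural patient whose catheter cannot be placed and who gets neither technique, and names no arm if cryoanalgesia is given instead

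*Combined protocol and SAP*

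**What the plan says.** Section 14.1 is the only place where the set to be analysed is defined. Beyond eligibility and randomisation, it includes patients who "receive at least the initial analgesic application (cryoanalgesia or epidural catheter placement) and undergo Nuss procedure will be included in the analysis".

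The order of events is clear from three other sections:

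- Section 8.1: "The envelope associated with each patient number is opened on the morning of surgery, revealing their group assignment".
- Section 10.2 lists the opening of the envelope as the second step at the time of surgery. The third is "Initial analgesic application (cryoanalgesia or epidural) and Nuss procedure".
- Section 8.3.2: "Thoracic epidural catheter will be placed by the pediatric anesthesia team prior to Nuss procedure".

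Section 5.1 defines the primary endpoint as "Hospital length of stay, measured from time of surgery to time of discharge". Section 8.4 provides that before each operation "both the AtriCure Cryosurgical system and supplies for thoracic epidural will be made available in the operating room".

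Sections 12, 13, 14.3 and 14.4 do not say in which arm a patient is analysed when the technique given differs from the one assigned. The documents contain no intention-to-treat or as-treated statement. Section 14 promises a detailed SAP before the final analysis, which may modify the plan.

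**The concern.** Receiving the technique is an event after randomisation, in a trial where section 8.2 accepts that nobody can be blinded once the arm is revealed. Consider an epidural patient whose catheter cannot be placed.

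1. **Neither technique.** Surgery goes ahead with systemic analgesia only. The patient has had neither application, so fails the condition in 14.1, yet time from surgery to discharge is known in full. The exclusion therefore does not serve to handle missing data.
2. **The other technique.** Cryoanalgesia is given instead. The patient meets the condition, because either technique satisfies it, but the text names no arm.

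Cryoanalgesia that cannot be applied is the mirror case. A later rescue epidural is not affected, because that patient's initial application was cryoanalgesia.

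Whether a catheter can be placed is part of the epidural strategy. In case 1 all cryoanalgesia patients are compared with only those epidural patients in whom placement worked. If failure is related to length of stay, the estimate shifts, and the protocol's own background leaves the direction open. Section 1 says epidural has been shown, on limited data, "to be more effective than PCA alone for the first few postoperative days", which suggests that patients without it might stay longer. Of the later move off the epidural it says "This may increase length of stay, as it introduces an intermediate step prior to home oral regimen", which suggests that they might leave sooner. With 10 patients per arm and no replacement of withdrawals (section 12.4), one patient is a tenth of an arm.

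**Working it through.** **Inputs.** From section 14.5: epidural mean 7 days, SD 1.3, cryoanalgesia about 2 days shorter (so 5), alpha 0.05, power 90%, 18 patients needed, 20 enrolled. From section 4.1: 1:1 allocation, so 10 per arm. From section 14.3: two-sided unpaired t test. Assumed, because the documents give no figure: k = 0, 1 or 2 of 10 catheters fail, and the failed patients' mean stay L lies between 5 and 9 days, with the same SD of 1.3.

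**The plan's own figure.** The normal approximation gives n per arm = 2 × [SD × (z₀.₉₇₅ + z₀.₉₀) / difference]² = 2 × [1.3 × (1.960 + 1.282) / 2]² = 8.88, rounded up to 9 per arm. This reproduces the stated 18.

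**Power when patients are left out.** Noncentral t, with n₁ + n₂ − 2 degrees of freedom and noncentrality 2 / [1.3 × √(1/n₁ + 1/n₂)]:

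- 10 v 10: 90.2%
- 10 v 9: 88.4%
- 10 v 8: 86.1%

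**Case 1, neither technique.** Left out, the expected difference is 7 − 5 = 2.0 days. Kept in the epidural arm, it is [(10 − k) × 7 + k × L] / 10 − 5. For k = 1 and L = 5 this is (63 + 5)/10 − 5 = 1.8. The shift is k × (L − 7)/10, at most 0.2 day per patient over the assumed range. Power when kept, and how often the two rules disagree on p < 0.05, come from 100,000 simulated trials per row (normal stays, pooled-SD t test):

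| k | L (days) | Difference, kept | Power, kept | Power, left out | Rules disagree |
|---|---|---|---|---|---|
| 1 | 5 | 1.8 | 80.0% | 88.4% | 9.4% |
| 1 | 7 | 2.0 | 90.3% | 88.4% | 3.8% |
| 1 | 9 | 2.2 | 93.2% | 88.4% | 5.0% |
| 2 | 5 | 1.6 | 67.0% | 86.1% | 20.0% |
| 2 | 7 | 2.0 | 90.1% | 86.1% | 6.5% |
| 2 | 9 | 2.4 | 95.6% | 86.1% | 9.7% |

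The rows with L = 7 show the disagreement that comes only from dropping patients, with no bias.

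**False positives in case 1.** With a mean of 7 days in both arms, removing epidural patients at random leaves the rate at 5.1% (k = 1) and 5.0% (k = 2). Removing the longest one or two epidural stays raises it to 7.4% and 11.6%, with shifts of 0.22 and 0.41 day. That is an extreme bound: placement fails before surgery and cannot select perfectly on a stay not yet observed.

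**Case 2, cryoanalgesia instead.** Failed patients are taken to stay 5 days on average.

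| k | Analysed as randomised | Analysed by technique received |
|---|---|---|
| 1 | 1.8 days, power 80.2% | 2.0 days, power 89.8% (11 v 9) |
| 2 | 1.6 days, power 66.8% | 2.0 days, power 89.0% (12 v 8) |

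**The case against.** The strongest reply is that this depends on an event the protocol does not describe. There is no failure rate and no stated path from a failed catheter to systemic analgesia alone. Both techniques are at hand, so a patient who gets neither is a narrow case. This stands as a limit on how likely the problem is. It does not change what 14.1 does when the case occurs.

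It can also be said that requiring receipt of the initial treatment is a common prespecified set, and that the synopsis objective speaks of patients receiving each technique. That makes the point a choice of what to estimate and not an arithmetical error, which is fair. But the choice conditions on an event after an unmasked allocation and discards an observed outcome, for no gain that the protocol states.

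Three smaller points:

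- A failed attempt might be held to count as placement. The plain reading is that it does not; if attempts are meant, the text should say so.
- For case 2, section 8.1 defines the groups by the envelope and section 14.4 tabulates by treatment group, so the randomised arm is the natural reading. This stands: taken alone, that half asks only for a clarification.
- The later SAP could settle both points. True, but unless it does, 14.1 governs, and the rule is better fixed before any failure occurs.

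The largest figures do come from corners of the assumed range. The 20% disagreement needs two failures whose patients go home as early as if they had had cryoanalgesia.

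**Conclusion.** The concern holds. Followed as written, section 14.1 removes a randomised patient with a complete primary outcome because of something that happens after the arm is revealed, and it leaves the arm of a patient who changes technique to inference.

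The effect is modest: at most 0.2 day per failed patient against a planned difference of 2 days, in a direction that cannot be known in advance. Leaving out one or two patients costs about 2 or 4 points of power. The size rests on the assumed 0 to 2 failures and the assumed 5 to 9 day stay; with no failures there is no effect, and if failure is unrelated to stay only patients are lost. Case 1 is the substance of the point. It is a change to consider, with medium confidence, and does not by itself undermine the trial.

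**What to change.** In section 14.1, or in the later SAP, delete the condition on the initial analgesic application and state the arm:

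> All eligible randomised patients who undergo the Nuss procedure are included. Patients are compared in the arm to which they were randomised, whatever technique or rescue they receive.

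The condition on the Nuss procedure should stay, because the endpoint is undefined without surgery. An analysis by technique received can be added as a sensitivity analysis.

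The cost is two sentences, with no added patients, visits or data. There is one downside. If failed-catheter patients go home sooner than other epidural patients (mean 5 days), keeping them lowers power to 80% with one such patient or 67% with two, against 88% or 86% if they are left out. That lower figure reflects the smaller difference between the two strategies as assigned.
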